### 9.3.2 Exclusion Criteria

Subjects who meet any of the following criteria will be excluded from this study:

1. Subjects who present only simple partial seizures without motor signs
2. Subjects who have seizure clusters where individual seizures cannot be counted
3. Subjects who present or have a history of Lennox-Gastaut syndrome
4. Subjects who have a history of status epilepticus within 1 year prior to Day 1 of the Treatment Phase
5. Subjects who have a history of psychogenic non-epileptic seizures within 5 years prior to Day 1 of the Treatment Phase
6. Subjects who have a history of suicidal ideation/attempt within 5 years prior to Day 1 of Treatment Phase
7. Subjects who present clinically problematic psychological or neurological disorder(s)
8. Evidence of clinically significant disease (eg, cardiac, respiratory, gastrointestinal, renal disease) that in the opinion of the investigator(s) could affect the subject's safety or interfere with the study assessments
9. Evidence of clinically significant active hepatic disease.
10. A prolonged QTcF interval (>450 ms [2 or 3 times]) as demonstrated by a repeated (3 times) electrocardiogram (ECG)
11. Subjects who have a history of receiving any AEDs (except for AEDs used as rescue treatment), antipsychotics or anti-anxiety drugs within 12 weeks prior to the Pretreatment Phase
12. Subjects who have not used a stable dose of antidepressant in the 12 weeks prior to the Pretreatment Phase, if they treat
13. Subjects who have a history of any type of surgery for brain or central nervous system within 1 year prior to the Pretreatment Phase

14. Subjects who have a history of receiving any AED (including AED used as rescue treatment) for more than 2 weeks in total within 2 years prior to the Pretreatment Phase
15. Subjects who have used intermittent rescue medicine on 2 or more occasions within 4 weeks before the Pretreatment Phase (1 to 2 doses over a 24-hour period considered one-time rescue)
16. Subjects who have a history of receiving any AED polytherapy
17. Subjects who experienced treatment with perampanel
18. Subjects who have had non-constant ketogenic diet within 4 weeks before the Pretreatment Phase
19. Subjects who have a history of drug or alcohol dependency or abuse within the last 2 years before the Pretreatment Phase
20. Subjects who have had multiple drug allergies or a severe drug reaction to an AED(s), including dermatological (eg, Stevens-Johnson syndrome), hematological, or organ toxicity reactions
21. Females who are breastfeeding or pregnant in the Pretreatment Phase (as documented by a positive beta-human chorionic gonadotropin [ $\beta$ -hCG] test)
22. Females of childbearing potential who:
  - Within 28 days before the start of the Pretreatment Phase, did not use a highly effective method of contraception, which includes any of the following:
    - total abstinence (if it is their preferred and usual lifestyle)
    - an intrauterine device or intrauterine hormone-releasing system (IUS)
    - a contraceptive implant
    - an oral contraceptive (with additional barrier method) (Subject must be on a stable dose of the same oral contraceptive product for at least 28 days before dosing and throughout the study and for 28 days after study drug discontinuation.)
    - have a vasectomized partner with confirmed azoospermia.
  - Do not agree to use a highly effective method of contraception (as described above) throughout the entire study period and for 28 days after study drug discontinuation.

It is permissible that if a highly effective method of contraception is not appropriate or acceptable to the subject, then the subject must agree to use a medically acceptable method of contraception, ie, double-barrier methods of contraception such as condom plus diaphragm or cervical/vault cap with spermicide.

NOTE: All females will be considered to be of childbearing potential unless they are postmenopausal (amenorrhic for at least 12 consecutive months, in the appropriate age group, and without other known or suspected cause) or have been sterilized surgically (ie, bilateral tubal ligation, total hysterectomy, or bilateral oophorectomy, all with surgery at least 1 month before dosing).

23. Subjects who have participated in a study involving administration of an investigational drug or device within 4 weeks before Visit 1, or within approximately 5 half-lives of the previous investigational compound, whichever is longer.

## 24. Subject who is diagnosed with dementia

### 9.3.3 Removal of Subjects From Therapy or Assessment

The investigator may withdraw the subject from the study at any time for safety or administrative reasons. The subject may stop study drug or withdraw from the study at any time for any reason.

A subject who discontinues study treatment should be followed for subsequent protocol-specified visits and procedures. The primary reason for discontinuation contributing to the subject's discontinuation from study drug(s) should be collected. If subjects need to take other AEDs because of insufficient efficacy of perampanel, they will discontinue the study. The first date when other AEDs are administered will be defined as the final date of perampanel monotherapy, and the subsequent date when the perampanel is completely withdrawn will be defined as the discontinuation date of the study.

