### **8.2 Secondary Objectives**

- To evaluate the seizure-free rate of the 52-week treatment in untreated patients with POS
- To confirm time to first seizure onset and time to withdrawal from the study from the first date of the Maintenance Period in untreated patients with POS
- To evaluate the safety and tolerability of perampanel monotherapy in untreated patients with POS

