## [8 mg Treatment Phase]

In the 8 mg Titration Period (4 weeks), subjects will be administered 6 mg QD of perampanel for 2 weeks and then will be up titrated to 8 mg QD and will continue for 2 weeks. If subjects have no safety issues at the end of the Titration Period, they will start the 8 mg Maintenance Period for 26 weeks.

If subjects don't tolerate 8 mg administration of perampanel, they will be able to down-titrate to 6 mg in accordance with the investigators' discretion. After the down-titration, subjects could continue the study with 6 mg QD.

If subjects experience the occurrence of seizures or could not continue 8 mg (or 6 mg) dosing due to intolerable adverse event during the 8 mg Maintenance Period, they will end the Treatment Phase.

A taper will be allowed at the investigator's discretion upon early discontinuation of the study.

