#### 9.4.7.1 Prohibited Concomitant Therapies and Drugs

##### 9.4.7.1.1 PROHIBITED CONCOMITANT DRUG

Throughout the study period, concomitant use of the following drugs is prohibited (till the visit at the time of early discontinuation for discontinued subjects).

- Other AEDs (if emergency care is needed, eg, status epilepticus, uncontrolled seizures, or clusters, occasional use (prn) of other AEDs including diazepam, phenytoin will be permitted as rescue treatment)
- The following drugs or food known to induce CYP3A (not limited to these drugs or food). If one of these drugs was being used at enrollment, washout of the drug will start at this time point. The duration of washout of the drug must be at least 2 weeks.  
[carbamazepine, enzalutamide, mitotane, phenytoin, phenobarbital, amobarbital, secobarbital, rifabutin, rifampicin, food containing St. John's Wort (*hypericum perforatum*), bosentan, efavirenz, etravirine, modafinil, armodafinil, rufinamide, nevirapine, oxcarbazepine, and glucocorticoid (except for topical use)]
- Antipsychotics
- Antianxiety drugs
- Benzodiazepine hypnotic
- Other investigational agents
- Antidementia drugs

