8.1 General Data Handling

Definition of Baseline data

Baseline is defined as the last non-missing value observed on or prior to the first study drug dispensing date.

Definition of Change from Baseline, Percent Change from Baseline

- Change from baseline = Post-baseline value - Baseline value
- % Change from baseline = (Change from baseline / Baseline value) * 100

For any baseline value of 0, the subject’s corresponding percent change from baseline will not be included in the summary statistics table.

Handling of data not within specified periods or within the follow-up period

Data obtained in the Follow-up Phase except for AE, Duration of Exposure and TEMAV will not be included in the summary tables. These data will be presented in the subject data listing.

Definition of End of Treatment

End of treatment phase during the 26-week Maintenance Period of the last evaluated dose is defined as the closest value observed on or post to the disposition date in the 26-week Maintenance Period of the last evaluated dose. If there is no adequate data, the closest value observed prior to the disposition date is selected.

End of treatment during the entire study (treatment phase or extension phase) is defined as the closest value observed on or post to the last disposition date in the entire study. If there is no data, the closest value observed prior to the last disposition date is selected.

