8.3 Safety Data Handling

Definition of derived variables for extent of exposure

The derivation rule will be presented in the [section 5.6.1](#).

Treatment-emergent adverse event

A treatment-emergent adverse event (TEAE) is defined as an AE that emerges during time from the first dose of study drug to the last visit or 28 days after the subject's last dose, whichever comes later, having been absent at pretreatment (Baseline) or

- Reemerges during treatment, having been present at pretreatment (Baseline) but stopped before treatment, or
- Worsens in severity during treatment relative to the pretreatment state, when the AE is continuous.

TEMAV (Treatment-Emergent Markedly Abnormal Value)

A TEMAV is defined as follows:

- For a phosphate, if the post baseline grade increases from baseline and the post baseline grade is greater than or equal to 3 then a value will be determined to be a TEMAV.
- For all other parameters presented in the [section 13.1](#), if the post baseline grade increases from baseline and the post baseline grade is greater than or equal to 2 then a value will be determined to be a TEMAV.

If the grade of baseline value is missing, then, if the grade of post-baseline value is Grade 2 or higher, the laboratory values will be classified into treatment emergent markedly abnormal.

Laboratory values, Vital signs, ECGs

For the end of treatment, the closest value measured on or post to the last disposition date in the Treatment Phase and the entire study period will be imputed using Last Observation Carried Forward (LOCF) method. If there is no adequate data, the closest value observed prior to the disposition date is selected.

Handling of below lower quantification values in laboratory results

In the cases where laboratory result contains below lower quantification (BLQ) value, it will be replaced to the lower limit value of quantification (LLOQ) for summary tables.

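### The protocol defines a final date of perampanel monotherapy, but no planned safety summary stops at, or flags events after, that date

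*Protocol*

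**What the plan says.** **End of monotherapy.** For a subject who needs another AED because perampanel is insufficiently effective, Protocol 9.3.3 sets two dates in sequence. The first is the end of monotherapy: "The first date when other AEDs are administered will be defined as the final date of perampanel monotherapy". The second comes later: "the subsequent date when the perampanel is completely withdrawn will be defined as the discontinuation date of the study". The protocol thus foresees an interval on perampanel plus another AED.

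**When another AED may start.** Protocol 9.4.7.1.1 bans other AEDs, apart from emergency rescue use, only "till the visit at the time of early discontinuation for discontinued subjects". Protocol 9.4.1 adds: "A taper will be allowed at the investigator's discretion upon early discontinuation of the study". No taper length is given. Under Protocol 9.1.4 the follow-up visit falls 4 weeks after the last tapered dose.

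**Safety windows.** SAP 8.3, like Protocol 9.7.1.8.2, counts as treatment-emergent an event that "emerges during time from the first dose of study drug to the last visit or 28 days after" the last dose, whichever is later. SAP 8.1 states: "Data obtained in the Follow-up Phase except for AE, Duration of Exposure and TEMAV will not be included in the summary tables". SAP 5.6.3 summarises TEMAVs over the whole study including Follow-up, and also for the Treatment Phase and for the entire study period.

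**Purpose of the data.** Protocol 8.2 gives the secondary safety objective as "To evaluate the safety and tolerability of perampanel monotherapy in untreated patients with POS". Protocol 7.2 plans to compare these safety data with the adjunctive-therapy study (Study 335) and to judge monotherapy safety signals from that comparison.

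**The concern.** The protocol defines the date on which monotherapy ends, and the SAP's safety sections never refer to it. A subject who leaves and starts another AED stays in the TEAE window through any overlap or taper and the weeks that follow. An event that begins then may belong to the new drug, to the combination, to perampanel or its withdrawal, or to none of these. The all-cause tables do not separate these cases. The TEAE table by dose does not help, because for the entire study period it assigns each event to the perampanel dose at or before onset and takes no account of a second drug.

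At stake is how cleanly the tables describe monotherapy. The planned contrast is with an adjunctive study, so time on perampanel plus another AED blurs the distinction being examined. With about 80 subjects, a single case is visible in a sparse row such as a hepatic or cardiac special-interest category.

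**Working it through.** The documents state no figure on this point, so the check sets the rules side by side and then does simple arithmetic.

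**Step 1: one subject's timeline.** Let A be the first date on another AED, B the last perampanel dose, and C the end of the TEAE window.

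- Protocol 9.3.3: monotherapy ends at A, and perampanel is fully withdrawn later, so A comes before B.
- SAP 8.3: C is the later of the last visit or B + 28 days.
- Time inside the window after monotherapy has ended: C − A ≥ (B − A) + 28 days.
- If another AED starts d days after the last perampanel dose, the 28-day limit leaves 28 − d days. Protocol 9.3.3 does not describe this case, but it can occur in a subject who leaves for intolerability.

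**Step 2: which summaries can count onset after A.**

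| Summary | Onset after another AED can be counted? |
|---|---|
| All-cause TEAEs, including serious TEAEs, entire study period | Yes; no cut at A, and Follow-up AEs are kept |
| All-cause TEAEs, Treatment Phase | Only for subjects who leave directly from that phase; an AED added in the Extension Phase adds nothing |
| Treatment-related TEAEs | Limited; events the investigator attributes only to the new drug are left out |
| TEAEs leading to discontinuation, reduction or interruption of perampanel | Not for an event that begins after perampanel has stopped |
| TEMAVs including Follow-up | Yes |
| TEMAVs, Treatment Phase and entire study period | Little; these appear to leave out Follow-up, since SAP 5.6.2 defines the entire period as the Treatment Phase or the Extension Phase |

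**Step 3: TEMAV observation time.** Protocol Tables 3 to 5 schedule laboratory tests at the early discontinuation visit and at Follow-up. The AED ban runs to the early discontinuation visit, so that sample should normally precede the new drug. That leaves one scheduled sample, at Follow-up, plus any unscheduled visit.

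**Step 4: direction.** Incidence is the number of subjects with an event divided by the fixed Safety Analysis Set. Compared with a table cut at A, a longer window can add subjects to the numerator and cannot remove any.

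**Step 5: size.** The planned number is 80, so one subject is 1/80 = 1.25 percentage points. Anything more needs assumptions. Let k subjects start another AED, with an overlap of t weeks before the last dose.

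- Subject-weeks after monotherapy = k × (t + 4). For k = 5, t = 0: 5 × 4 = 20. For k = 30, t = 4: 30 × 8 = 240.
- For one preferred term with assumed on-monotherapy incidence p = 10% and assumed chance q of a first such event after A, reported incidence = p + (k/80)(1 − p)q.
- k = 5, q = 5%: 0.10 + 0.0625 × 0.90 × 0.05 = 0.1028, or 10.3%.
- k = 30, q = 20%: 0.10 + 0.375 × 0.90 × 0.20 = 0.1675, or about 16.8%. This needs 30 × 0.90 × 0.20 = 5.4 subjects with new onset of the same term.

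The documents give none of k, t, p or q. The range shows how the mechanism works and is not an estimate.

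**The case against.** The strongest defence is that a window to 28 days after the last dose is a common safety convention and matches the SAE collection period in Protocol 9.5.1.5.1. TEAE is a temporal definition that claims no cause. The safety analysis is descriptive, and no efficacy conclusion depends on it. All adverse events and medications are listed, so about 80 subjects can be traced by hand. All of this stands, and the existing window should stay. But hand tracing is not a prespecified summary, and the causality question in Protocol 9.5.1.5.1 asks only whether the study drug may have caused the event, so it does not separate perampanel from a co-administered AED.

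A reader might make three stronger inferences, none of which the documents support:

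- *Every TEAE and TEMAV table is contaminated.* The Treatment Phase, treatment-related and discontinuation tables, and the two further TEMAV summaries, limit or avoid the problem, as set out in the table above.
- *Incidences are overstated by several points.* Assuming that 15% to 30% of 80 subjects start another AED and that 10% to 30% of those have a new event gives 12 × 0.10 = 1.2 to 24 × 0.30 = 7.2 subjects, or 1.5% to 9.0% of 80. None of these inputs has a source in the documents. The result also pools different events, while the tables count each subject once per SOC and preferred term.
- *Monotherapy safety should be judged only on tables cut at the first other AED.* That would drop taper, withdrawal and delayed perampanel events, and only in subjects who leave. The SAP itself searches for drug abuse, dependence and withdrawal terms as a special interest.

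**Conclusion.** The gap is real but narrow: a protocol-defined date that bears directly on a secondary objective is used by no safety summary. Through the window and Follow-up rules, the all-cause TEAE summaries and the TEMAV summary that includes Follow-up can count events that begin after another AED has started.

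The conclusion on direction rests on the fixed denominator. The 1.25-point unit rests on the planned 80 subjects and changes with the actual Safety Analysis Set.

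Two limits on the date itself carry over to the fix. Protocol 9.3.3 is written for subjects who need another AED for insufficient efficacy, so it does not clearly cover those who leave for intolerability. It also does not say whether permitted rescue use ends monotherapy.

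**What to change.** Leave all existing tables as they are. In SAP 8.3, 5.6.2 and 5.6.3:

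1. Derive a flag for TEAEs and TEMAVs with onset after the first non-rescue other AED, whatever the reason for leaving. Take the date from the concomitant medication CRF, which records start dates and reason for use (Protocol 9.4.7). Include AEDs that SAP 5.2.5 would class as post-treatment medications.
2. Add supplementary tables restricted to onset up to that date: TEAEs by SOC and preferred term, serious TEAEs, and TEMAVs.
3. List the later events with the AED concerned.
4. State that the restricted tables are reported alongside the full-window tables and do not replace them.

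The cost is SAP wording, one derived variable, a few tables and a listing. No new data are needed and patient care does not change. The downside is that the restricted tables omit taper, withdrawal and delayed perampanel events; the full-window tables still show these, so both sets must be read together.

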## 9.4 Treatment

### 9.4.1 Treatment Administered

#### Treatment Phase

The following treatment will be administered to subjects in the Treatment Phase (Table 1). Perampanel is orally administered once a day before bedtime.

[4 mg Treatment Phase]

In the 4 mg Titration Period (6 weeks), subjects will initiate 2 mg QD of perampanel for 2 weeks and then will be up-titrated to 4 mg QD and will continue for 4 weeks. If subjects have no safety issues at the end of the Titration Period, they will start the 4 mg Maintenance Period for 26 weeks.

If subjects experience seizures during the 4 mg Maintenance Period, the investigator will end the 4 mg Maintenance Period and judge the transition to the 8 mg Titration Period based on the subject's tolerability and safety. If subjects could not continue 4 mg dosing due to intolerable adverse event during the 4 mg Maintenance Period, they will discontinue the study.

During the 2 weeks of Weeks 3 and 4 in the 4 mg Titration Period, if subjects are suspected to have tolerability issues for 4 mg dosing due to occurrence of adverse events, 2 mg QD can be administered in accordance with the investigators' discretion. In that case, subjects will visit the investigational site via unscheduled visit within 4 weeks after starting study treatment and will be up-titrated to 4 mg QD (for subjects who has continued 4 mg QD, occurrence of AEs will be confirmed via telephone). All subjects will continue 4 mg QD during the 2 weeks of Weeks 5 and 6. If subjects could not continue 4 mg QD due to intolerable adverse event, they will discontinue the study.

## [8 mg Treatment Phase]

In the 8 mg Titration Period (4 weeks), subjects will be administered 6 mg QD of perampanel for 2 weeks and then will be up titrated to 8 mg QD and will continue for 2 weeks. If subjects have no safety issues at the end of the Titration Period, they will start the 8 mg Maintenance Period for 26 weeks.

If subjects don't tolerate 8 mg administration of perampanel, they will be able to down-titrate to 6 mg in accordance with the investigators' discretion. After the down-titration, subjects could continue the study with 6 mg QD.

If subjects experience the occurrence of seizures or could not continue 8 mg (or 6 mg) dosing due to intolerable adverse event during the 8 mg Maintenance Period, they will end the Treatment Phase.

A taper will be allowed at the investigator's discretion upon early discontinuation of the study.

**Table 1 Treatment Administered (Treatment Phase)**

| Treatment Phase         | Week         | Day           | Dose              | Frequency and Number Dispensed     |
|-------------------------|--------------|---------------|-------------------|------------------------------------|
| 4 mg Titration Period   | Weeks 1 – 2  | Days 1 – 14   | 2 mg              | QD, 1 × 2 mg tablet before bedtime |
|                         | Weeks 3 – 6  | Days 15 – 42  | 4 mg              | QD, 2 × 2 mg tablet before bedtime |
| 4 mg Maintenance Period | Weeks 7 – 32 | Days 43 – 224 | 4 mg              | QD, 2 × 2 mg tablet before bedtime |
| 8 mg Titration Period   | Weeks 1 – 2  | Days 1 – 14   | 6 mg              | QD, 3 × 2 mg tablet before bedtime |
|                         | Weeks 3 – 4  | Days 15 – 28  | 8 mg              | QD, 4 × 2 mg tablet before bedtime |
| 8 mg Maintenance Period | Weeks 5 – 30 | Days 29 – 210 | 8 mg a | QD, 4 × 2 mg tablet before bedtime |

QD = once daily.

## Extension Phase

Subjects who complete the 26-week Maintenance Period will continue the last dose of the Maintenance Period. Subjects who end the Treatment Phase due to insufficient efficacy or safety issue before the completion of the 26-week Maintenance Period will adjust their appropriate dose (within 4 – 8 mg of perampanel) and continue the Extension Phase. Subjects will be allowed to adjust within 2 – 8 mg of perampanel with investigators' consideration for their condition of the seizures and/or tolerability. During whole study period, the maximum dose of perampanel is 8 mg QD. The dose will be increased at intervals of 1 week or more in increments of 2 mg.

[figure not shown]
